## 1. Study Synopsis

|  |   |
|--|---|
| Title of clinical study                          | An observational, prospective study to assess the outcomes of different treatment options in patients with chronic venous disease in Belgium  |
| Protocol Short Title/Acronym                     | Venous Outcome Study (VOS)  |
| Sponsor name                                     | KU Leuven   |
| Coordinating Investigator                        | [name] PhD
Department of Cardiovascular Sciences
Research Unit Vascular Surgery
KU Leuven, Leuven, Belgium   |
| Medical condition or disease under investigation | Chronic Venous Disease (CVD)  |
| Purpose of clinical study                        | This study aims to describe conservative and invasive treatments for patients with CVD in Belgium, and their association with clinical and patient-reported outcomes.   |
| Primary objective                                | To assess the evolution of the Quality of Life (QoL) after 12 weeks for patients with CVD who underwent conservative or invasive treatment.   |
| Secondary objectives                             | 
 
1. To describe patient characteristics by treatment group, including demographic characteristics, clinical characteristics and specific comorbidities at the inclusion visit (V0), and risk factors and treatment characteristics per visit.
 
2. To estimate the proportion of patients who received an intervention as secondary/add-on treatment to conservative treatment or who received a re-intervention, and the time to secondary/add-on intervention or re-intervention.
 
 |

|   |   |
|---|---|
|   | 
 
3. To assess the evolution of the QoL over time by treatment.
 
4. To assess the evolution of the clinical part of the Clinical Etiological Anatomic Pathophysiologic (CEAP) classification over time by treatment.
 
5. To assess the evolution of patient's signs through physician-assessed revised Venous Clinical Severity Score (rVCSS) over time by treatment.
 
6. To assess the evolution of patient's assessment of symptom severity over time by treatment.
 
7. To assess the evolution of patient satisfaction over time by treatment.
 
8. To assess QoL, signs, symptoms and patient satisfaction of patients who received an intervention as secondary/add-on treatment to conservative treatment.
 
9. To assess the safety of treatments in patients with CVD.
 
  |
| 
Study Design
 | 
This study is an observational, prospective, multicentre study to assess the effectiveness of conservative and invasive treatments in patients with CVD in Belgium. The inclusion period of the study will last 6 months. Patients will be followed until 2 years after inclusion into the study.
 
During the inclusion period, after confirmation of eligibility, patients with CVD diagnosed by the General Practitioner (GP) and requiring a treatment will be invited to participate in the study. About 120 GPs across Belgium will be included in the study. During the VO, a treatment strategy will be proposed to the patient by the GP. The treatment can be conservative or invasive, depending on the severity of the disease. Patients awaiting invasive treatment may receive conservative treatment to alleviate symptoms. The choice of treatment modality is left to the discretion of the treating physician, in agreement with the patient and according to local policies. As this is an observational study, there will be no interference in the choice of treatment, and no restrictions will be imposed.
 |

|                  |  |
|------------------|--|
|                  | 
Patients and their GP may decide to switch at any time between conservative treatments or to undergo an intervention as secondary/add-on treatment to conservative treatment.
 
Baseline data will be collected by the GP on the day of the V0. Follow-up visits will be organized by the GP at defined timepoints after the V0: at 6 weeks, 12 weeks, 6 months, 12 months and 24 months of follow-up (V1-V5).
 
A delay between referral to the venous centre during the V0 and the day of invasive treatment is anticipated. To allow assessment of the primary study objective, GPs will be asked to invite the patients for a follow-up visit 12 weeks after the invasive treatment took place (V-i), provided that it falls within the scope of routine medical practice in terms of visit frequency.
 
Due to the real-world setting, patients might not be assessed exactly at the proposed weeks/months. Therefore, some visits may not take place if they are not within the scope of regular medical practice. Additionally, a time range around the visits will be allowed.
 |
| 
Endpoints
 | 
Primary endpoint:
 
The primary endpoint is the change in the Global Index Score (GIS) of the Chronic Venous Insufficiency Quality of life questionnaire (CIVIQ-20) from V0 to a visit realized 12 weeks after the beginning of the treatment (or day of the intervention for patients in the invasive groups).
 
Secondary endpoints:
 
 
1. Description of patient characteristics by treatment group at V0 (demographics, clinical characteristics, history of CVD, treatment history, specific comorbidities) and description of risk factors and treatment characteristics per visit (type of treatment [initial referral from GP and whether they actually
 
  |

|  |   |
|--|---|
|  | 
received the treatment], concomitant treatment, compliance with conservative treatment)
 
 
2. Proportion of patients who received an intervention as secondary/add-on treatment to conservative treatment (in the conservative treatment group). Proportion of patients who received a re-intervention (in the invasive treatment group) and number of re-interventions. Time to secondary/add-on intervention or re-intervention.
 
3. The change in the GIS of CIVIQ-20 over time from V0 to each follow-up visit.
 
4. The change in the clinical part of the CEAP classification over time from V0 to each follow-up visit.
 
5. The change in the rVCSS over time from V0 to each follow-up visit.
 
6. The change in the symptomatology over time from V0 to each follow-up visit.
 
7. The change in satisfaction score over time from V1 to each follow-up visit.
 
8. The change in CIVIQ-20, CEAP, rVCSS, symptomatology and satisfaction scores in patients who received an intervention as secondary/add-on treatment to conservative treatment.
 
9. Number and proportion of patients with Adverse Events (AEs).
 
 |
| 
Sample Size
                     | 
Considering a Minimum Clinically Important Difference (MCID) of 5 points before/after treatment for the primary endpoint, a default correlation of 0.5, and with an expected drop-out of 60% of patients in the conservative group and 25% in the invasive group, we propose the recruitment of 1650 patients (safe margin), to finally include minimally 1590 patients (power 90%).
 
Each investigator (120 GPs) will recruit approximately between 10 and 15 consecutive patients.
   |
| 
Summary of eligibility criteria
 | 
Inclusion criteria
 
 
• Patient visiting a GP with complaints related to CVD,
 
  |

|  |   |
|--|---|
|  | 
 
• Patient aged <math>\geq 18</math> years old at inclusion,
 
• Patient receiving the diagnosis of CVD from the GP during the VO, according to international guidelines and made on a clinical basis,
 
• Patient requiring and agreeing to receive conservative or invasive treatment,
 
• French or Dutch speaking patient,
 
• Patient signed informed consent and agrees to take part in the study and follow-up.
 
 
Exclusion criteria
 
 
• Patient with coagulation disorders such as thrombophilia and/or taking anticoagulation drugs,
 
• Pregnant or breastfeeding patient,
 
• Patient with severe Peripheral Arterial Occlusive Disease (POAD), with Ankle Brachial Index (ABI) <math>< 0.8</math>,
 
• Patient with malignancy,
 
• Patient with neurological disorder or dementia,
 
• Patients taking regular treatment for CVD 3 months prior to inclusion (except painkillers or anti-inflammatory drugs if taken for reasons other than CVD),
 
• Patient in any other clinical study for any pharmaceutical product within 4 weeks preceding study inclusion,
 
• Patient with any comorbidity or situation preventing a follow-up of 2 years.
 
 |
| Maximum duration of treatment of a patient | 
The duration of treatment is the day(s) of the intervention for the invasive treatment group.
 
The maximum duration of treatment is 24 months for the conservative group.
  |
| Version and date of final protocol         | Final version of the protocol V1.2 (07-Aug-2023)  |
| Version and date of protocol amendments    | Not applicable  |

## 2. List of abbreviations

|          |  |
|----------|--|
| AE       | Adverse Event  |
| AS       | Analysis Set   |
| BMI      | Body Mass Index  |
| CEAP     | Clinical Etiological Anatomic Pathophysiologic             |
| CIVIQ-20 | Chronic Venous Insufficiency Quality of life questionnaire |
| CRA      | Clinical Research Associate                                |
| CRO      | Contract Research Organisation                             |
| CVD      | Chronic Venous Disease                                     |
| eCRF     | electronic Case Report Form                                |
| GCP      | Good Clinical Practice                                     |
| GIS      | Global Index Score   |
| GP       | General Practitioner                                       |
| ICF      | Informed Consent Form                                      |
| ICH      | International Conference on Harmonisation                  |
| (I)EC    | (Independent) Ethics Committee                             |
| IS       | Included Set   |
| MCID     | Minimum Clinically Important Difference                    |
| MedDRA   | Medical Dictionary for Regulatory Activities               |
| QoL      | Quality of Life  |
| RCT      | Randomised Controlled Trial                                |
| rVCSS    | revised Venous Clinical Severity Score                     |
| SAE      | Serious Adverse Event                                      |
| SAP      | Statistical Analysis Plan                                  |
| SOP      | Standard Operating Procedure                               |
| TEAE     | Treatment Emergent Adverse Event                           |
| V        | Visit  |
| VO       | Inclusion Visit  |
| VAS      | Visual Analogue Scale                                      |
| VOS      | Venous Outcome Study                                       |

### 3. Background and rationale

Chronic Venous Disease (CVD) is one of the most common disorders worldwide, with a total prevalence of more than 50% in the adult population (Vuylsteke 2018). CVD is defined as any morphological and functional abnormality of the venous system. It includes a spectrum of clinical presentations ranging from uncomplicated telangiectasias and varicose veins evolving to skin changes and venous ulceration.

In order to report the extent of the venous disease, a scoring system was introduced in 1994 and updated in 2004 and 2020 (Beebe 1996, Porter 1995, Eklöf 2004, Lurie 2020). This classification is based on clinical manifestations (C), etiological factors (E), anatomic distribution of the disease (A) and underlying pathophysiological findings (P), and is a descriptive classification (CEAP score). In most studies, only the C-classification is used, varying from C0 to C6. The term CVD includes stages C1-C6, whilst Chronic Venous Insufficiency (CVI), usually reserved for more advanced venous disease, includes oedema, skin changes and venous ulcers (C3-C6) (Eklöf 2008, De Maeseneer 2019).

Untreated CVD will evolve into more severe stages. The underlying mechanism of this progression is persistent venous hypertension and local inflammation of the vessel wall. Epidemiological data show an association between several risk factors and CVD progression. Some of them, mostly lifestyle-related, can be modified. However, the most important risk factors are not modifiable, such as having a positive family history, age and sex (Vuylsteke 2018). The progression rate to a higher clinical stage reaches 4% each year (Pannier 2012). Half of the patients with unilateral varicose veins will develop CVD on the contralateral leg in 5 years (Kostas 2010). One third of the patients with varicose veins will develop skin changes over a period of 13 years (Lee 2015). The development of more signs and symptoms impacts patients' health-related Quality of Life (QoL) (Kurz 2001).

Due to its high prevalence, impact on QoL, and morbidity and costs associated with advanced disease, CVD is associated with a large socioeconomic burden. In Western countries, where the prevalence of CVD is highest, it already consumes up to 2% of healthcare budgets (Davies 2019).

With progression to higher clinical stages of the disease, patients will seek appropriate treatment to alleviate symptoms. The treatment options nowadays are extended (Campbell 2020) and influenced by the disease severity, reimbursement policies, costs, geography and the preference of the surgeon (Guillaume 2020). Diminishing the signs and the symptoms of the disease, and preventing progression and recurrence are the main objectives for every treatment option. The treatment options range from conservative therapy, such as lifestyle changes, oral or topical venoactive drugs, or compression to more invasive treatments including sclerotherapy, surgery and endovenous techniques. Treatment guidelines have been prescribed according to the severity of the disease (Gloviczki 2011, Gloviczki 2012, Wittens 2015, Rabe 2013, Nicolaidis 2018, Nicolaidis 2020).

Several RCTs have provided evidence that venoactive drugs and compression therapy may reduce symptoms of CVD (Martinez-Zapata 2020, De Maeseneer 2022). The non-interventional, prospective

“VEIN Act Program” study has shown the effectiveness of conservative therapies to reduce CVD symptoms, but average follow-up was only 2.5 months (Bogachev 2019).

In order to evaluate the efficacy of the possible invasive treatments, a large number of Randomised Controlled Trials (RCTs) and meta-analyses have been conducted (Murad 2011, Siribumrunwong 2012, Hamann 2017). In many studies, anatomical success (occlusion rates) and postoperative side-effects such as pain, paraesthesia, and ecchymosis are the main outcomes. Surrogate outcomes, such as vein occlusion rates, stent patency, and changes in venous haemodynamics do not necessarily relate to a clinical change. In contrast, the number of publications including symptomatology and QoL as an outcome are limited. Only few studies have a long-term follow-up (Murad 2011, Eklöf 2014, Brittenden 2019, Kheirelseid 2018). Some studies with longer follow-up show controversial results: less favourable anatomical results (duplex ultrasound) did not result in any difference in clinical and QoL outcomes (Hamann 2017).

More long-term longitudinal studies are needed, without interfering with current clinical practice, including a sufficient number of patients, investigating the evolution of symptomatology and QoL in patients undergoing treatment for CVD. To obtain in-depth insights into the evolution of outcomes in patients with CVD undergoing treatment in Belgium, we will conduct a longitudinal observational prospective study. This study aims to describe conservative and invasive treatments for patients with CVD in Belgium, and their association with clinical and patient-reported outcomes.

## 4. Study objectives and Design

### 4.1 Study objectives

The **primary objective** is to assess the evolution of the QoL after 12 weeks for patients with CVD who underwent conservative or invasive treatment.

The **secondary objectives** are:

1. To describe patient characteristics by treatment group, including demographic characteristics, clinical characteristics and specific comorbidities at the inclusion visit (V0), and risk factors and treatment characteristics per visit.
2. To estimate the proportion of patients who received an intervention as secondary/add-on treatment to conservative treatment or who received a re-intervention, and the time to secondary/add-on intervention or re-intervention.
3. To assess the evolution of the QoL over time by treatment.
4. To assess the evolution of the clinical part of the Clinical Etiological Anatomic Pathophysiologic (CEAP) classification over time by treatment.
5. To assess the evolution of patient’s signs through physician-assessed revised Venous Clinical Severity Score (rVCSS) over time by treatment.
6. To assess the evolution of patient’s assessment of symptom severity over time by treatment.
7. To assess the evolution of patient satisfaction over time by treatment.

8. To assess QoL, signs, symptoms and patient satisfaction of patients who received an intervention as secondary/add-on treatment to conservative treatment.
9. To assess the safety of treatments in patients with CVD.

#### 4.2 Primary endpoints

The primary endpoint is the change in the Global Index Score (GIS) of the Chronic Venous Insufficiency Quality of life questionnaire (CIVIQ-20) from V0 to a visit realized 12 weeks after the beginning of the treatment (or day of the intervention for patients in the invasive groups).

#### 4.3 Secondary endpoints

The secondary endpoints are:

1. Description of patient characteristics by treatment group at V0 (demographics, clinical characteristics, history of CVD, treatment history, specific comorbidities) and description of risk factors and treatment characteristics per visit (type of treatment [initial referral from General Practitioner (GP) and whether they actually received the treatment], concomitant treatment, compliance with conservative treatment).
2. Proportion of patients who received an intervention as secondary/add-on treatment to conservative treatment (in the conservative treatment group). Proportion of patients who received a re-intervention (in the invasive treatment group) and number of re-interventions. Time to secondary/add-on intervention or re-intervention.
3. The change in the GIS of CIVIQ-20 over time from V0 to each follow-up visit.
4. The change in the clinical part of the CEAP classification over time from V0 to each follow-up visit.
5. The change in the rVCSS over time from V0 to each follow-up visit.
6. The change in the symptomatology over time from V0 to each follow-up visit.
7. The change in satisfaction score over time from V1 to each follow-up visit.
8. The change in CIVIQ-20, CEAP, rVCSS, symptomatology and satisfaction scores in patients who received an intervention as secondary/add-on treatment to conservative treatment.
9. Number and proportion of patients with Adverse Events (AEs).

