#### **4.4.2 Study setting**

The GP examines the patient and makes the diagnosis of CVD, based on clinical signs and symptoms. Patients who receive a diagnosis of CVD according to international guidelines who require conservative or invasive treatment can be included in the study. Duplex ultrasound or any other specific examination is not required to make the diagnosis, but could be done if needed according to routine clinical practice and recommendations. Each participating GP (120 GPs) will select approximately between 10 and 15 patients with CVD.

During the inclusion visit (V0), a treatment strategy will be proposed to the patient with confirmed CVD by the GP. The treatment can be conservative or invasive, depending on the severity of the disease. Patients awaiting invasive treatment may receive conservative treatment to alleviate symptoms. The choice of treatment modality is left to the discretion of the treating physician, in agreement with the patient and according to local policies. As this is an observational study, there will be no interference in the choice of treatment, and no restrictions will be imposed.

Commonly proposed conservative treatment options include compression therapy, and oral or topical venoactive drugs. If the GP decides that the patient needs an invasive treatment, then the patient will be referred to a venous centre. The specialist to whom the patient is referred, chooses the type of invasive treatment, as done in standard clinical care. The specialist may also prescribe conservative treatment to the patient, either while awaiting invasive treatment or in case invasive treatment is not deemed necessary.

[figure not shown]
Patients and their GP may decide to switch at any time between conservative treatments or to undergo an intervention as secondary/add-on treatment to conservative treatment.

Baseline data will be collected by the GP on the day of the V0. Follow-up visits, which are expected to take place within the scope of routine clinical practice, will be organized by the GP at defined timepoints after the V0: at 6 weeks, 12 weeks, 6 months, 12 months and 24 months of follow-up (V1-V5).

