A delay between referral to the venous centre during the V0 and the day of invasive treatment is anticipated. To allow assessment of the primary study objective, GPs will be asked to invite the patients for a follow-up visit 12 weeks after the invasive treatment took place (V-i), provided that it falls within the scope of routine medical practice in terms of visit frequency.

Due to the real-world setting, patients might not be assessed exactly at the proposed weeks/months. Therefore, some visits may not take place if they are not within the scope of regular medical practice. Additionally, a time range around the visits will be allowed. The frequency of follow-up visits is upon the discretion of the treating physicians.

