7. The patient **satisfaction** rate: the patients provide a score from 0 (not satisfied) to 10 (very satisfied) regarding the result of the treatment offered for their CVD.
8. The CIVIQ-20, CEAP, rVCSS, symptomatology and satisfaction scores, as detailed above, in patients who received an intervention as secondary/add-on treatment to conservative treatment.
9. Assessment of AEs will be described in [Section 8](#).

All of these outcomes, except for treatment failure characteristics, satisfaction, and AEs, will be measured at V0. All outcome measures will be collected V1-V5 (6 weeks, 12 weeks, 6 months, 12 months and 24 months after the V0) and V-i (12 weeks after the day of invasive treatment).

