The change in the symptomatology over time from V0 to each follow-up visit will be evaluated with the same methods as the primary endpoints.

The satisfaction score over time from V1 to each follow-up visit will be described as a quantitative variable.

Number and proportion of patients with AEs will be described.

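### Secondary endpoint 7 is defined as a change in satisfaction from V1, but the analysis section describes the score itself, and invasive patients' ratings before and after the procedure are not separated

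*Protocol*

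**What the plan says.** Objective 7 (Protocol Section 4.1) is "To assess the evolution of patient satisfaction over time by treatment". Endpoint 7 (Section 4.3, repeated in the Synopsis) turns this into "The change in satisfaction score over time from V1 to each follow-up visit".

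Section 7 defines the measure: "the patients provide a score from 0 (not satisfied) to 10 (very satisfied) regarding the result of the treatment offered for their CVD". It also says that satisfaction has no inclusion-visit value: "All of these outcomes, except for treatment failure characteristics, satisfaction, and AEs, will be measured at V0". Table 1 agrees, with satisfaction first collected at V1. V1 is 6 weeks after V0 in both groups and is not tied to the start of treatment.

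On the invasive group, Section 4.4.2 states: "A delay between referral to the venous centre during the V0 and the day of invasive treatment is anticipated". The length of the delay is not given. The same section allows conservative treatment during the wait. It also adds a visit V-i, 12 weeks after the procedure, to be held only if it fits routine visit frequency.

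The only analysis text specific to satisfaction is in Section 9.3.3, under Secondary endpoints: "The satisfaction score over time from V1 to each follow-up visit will be described as a quantitative variable".

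**The concern.** Two things do not fit together.

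First, the endpoint is a change and the planned analysis is a level. In Section 9.3.3 the sentences on CIVIQ-20, CEAP, rVCSS and symptoms all speak of a change; the satisfaction sentence does not. A programmer or report author could produce either quantity and claim to follow the protocol.

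Second, the item asks for a rating "regarding the result of the treatment offered for their CVD", so its level is already the outcome. A change from V1 has no pre-treatment reference and cancels whatever satisfaction was reached by week 6. It also starts from a visit whose treatment status can differ between the groups: conservative patients may already be on treatment at V1, while invasive patients may or may not have had the procedure.

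At stake is how objective 7 is read by treatment group and overall. A figure for the invasive group, or for both groups pooled, could partly reflect how many patients were still waiting at a given visit.

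**Working it through.** The protocol gives no figure to reproduce here: no expected rating, no waiting time and no test. The check is mostly textual, with illustrations on assumed values.

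**1. Endpoint against analysis.** Section 4.3 and the Synopsis: change from V1. Section 9.3.3: the score from V1 onward, described as a quantitative variable. These are different quantities.

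**2. What a change from V1 removes.** Change = later score − V1 score. A patient rating 9 at every visit has 9 − 9 = 0; a patient rating 3 at every visit has 3 − 3 = 0. With a common later score of 8:

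| V1 score | Change from V1 |
|---|---|
| 8 | 0 |
| 7 | +1 |
| 5 | +3 |
| 3 | +5 |

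The same final satisfaction gives a different endpoint value according to the V1 rating. This is arithmetic and does not depend on any waiting time.

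**3. Patients without V1.** Section 4.4.2 accepts that some visits may not take place, and Section 9.3.2 admits a patient to the Analysis Set with V2 or V3 as the only follow-up visit. Such a patient has satisfaction ratings but no change from V1.

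**4. Invasive patients before the procedure at V1 (illustration).** Assume an exponential waiting time from V0. The share still waiting at week 6 is 2^(−6/median wait).

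| Assumed median wait (weeks) | Share before the procedure at V1 |
|---|---|
| 2 | 12.5% |
| 4 | 35.4% |
| 6 | 50.0% |
| 8 | 59.5% |
| 12 | 70.7% |

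**5. Effect on the change (illustration).** Suppose ratings are d points higher after the procedure than while waiting, and otherwise constant. Once all have been operated, the mean change from V1 is share × d. For d = 2 this gives 0.25, 0.7, 1.0, 1.2 and 1.4 points down the table; for d = 4 it gives 0.5, 1.4, 2.0, 2.4 and 2.8. A conservative group with a constant rating would show 0.

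**6. Effect on the level by visit (illustration).** Take a median wait of 6 weeks, a rating of 4 while waiting and 8 afterwards. At V1 the invasive mean is 0.50 × 4 + 0.50 × 8 = 6.0. At V2 the share waiting is 2^(−12/6) = 25%, so the mean is 0.25 × 4 + 0.75 × 8 = 7.0. The mean rises by one point although no operated patient's rating has changed. Describing the level therefore does not by itself separate the two kinds of rating.

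**The case against.** The strongest reply is that the planned output already does most of what is needed. Section 9.3.3 describes the score, with means, SDs and quartiles for continuous variables and results by treatment group. A reader might infer from the endpoint wording that a uniformly dissatisfied group would look the same in the report as a uniformly satisfied one. That does not follow: a group at 3 and a group at 9 would be reported as 3 and 9. Nor can one say that the study fails to measure satisfaction with treatment. The instrument asks about it directly; only the change from V1, read alone, is a poor measure of it.

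It is also fair that evolution over time is what objective 7 asks for, that the protocol never calls V1 a pre-treatment baseline, and that no between-group test of satisfaction is planned. A reader might go on to say that most conservative patients are on treatment at V1, or that V1 often precedes the procedure. Both are plausible, but the protocol gives no waiting time and no start-of-treatment distribution. A waiting patient may also be on conservative treatment, so a rating before the procedure can refer to a real treatment experience, though not to the result of the procedure.

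These replies limit the harm. They do not remove the mismatch between endpoint and analysis, and they do not separate invasive ratings made before and after the procedure.

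**Conclusion.** The point holds as a minor one. Endpoint 7 and its analysis name different quantities, and the one in the endpoint definition is the less suitable: it has no pre-treatment reference, subtracts satisfaction reached by week 6, is undefined without V1, and may start before the procedure in the invasive group. The planned by-visit description keeps the level but mixes ratings from before and after the procedure, which affects the invasive and pooled summaries.

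The mismatch and the cancellation rest on the text and arithmetic alone. The size of the mixing rests on an assumed exponential wait and assumed ratings, and is illustrative only. Its direction requires that ratings rise after the procedure. The endpoint is secondary and descriptive.

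**What to change.** In Section 4.3 and the Synopsis, restate endpoint 7 as the satisfaction score at each follow-up visit, reported as a level with its 95% confidence interval, to match Section 9.3.3.

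In Section 9.3.3, state that ratings made before the treatment was received are summarised separately from those made after it. The treatment start and intervention dates needed for this are already collected (Table 1, footnote c).

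Do not restrict invasive ratings to V-i and later. V-i is conditional, so some patients will not have it, and earlier post-procedure ratings would be lost. For example, a patient operated on at week 2 has V-i due at week 2 + 12 = 14, yet V1 (week 6) and V2 (week 12) both follow the procedure.

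If a within-patient change is wanted, start it from the first rating after treatment was received. Align endpoint 8, which names a change in satisfaction without a reference visit.

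Cost: wording and slightly more tabulation, with no new data. The downside is that there is no longer a single change-from-V1 figure.
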